### **Exposure**

Duration of exposure (in years) among patients receiving tafamidis while enrolled in THAOS will be summarized (excluding time when the patient was part of clinical trial or Compassionate Use/Early Access Program) by starting dose using the tafamidis treated set by phenotype at enrollment and overall, CCI [REDACTED] and either predominantly cardiac or mixed phenotype at enrollment, tafamidis treated set for patients who had severe hepatic impairment at baseline, tafamidis treated set by liver transplantation status (liver transplant prior to first dose of tafamidis/liver transplant after the first dose of tafamidis/no liver transplant).

Additionally the duration of treatment with 20 mg and 61 mg/80 mg will be summarized separately for patients with off label use.

The duration of exposure (in years) will be calculated as:

Sum of all non-missing days when tafamidis was taken (excluding days of other clinical trial/compassionate use participation) / 365.25

Summary of exposure-adjusted Incidence rates (per patient-year) AEs and SAE for Treatment Emergent Adverse events (All causalities) and mortality for tafamidis treated set will be provided.

A separate listing will be provided for duration of exposure listing for patients who switched from 61/80 mg to 20 mg.

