## 1 AMENDMENTS FROM PREVIOUS VERSION(S)

### Amendment 1

Section of the SAP	Summary of change	Rationale
2	Spacing issue resolved	Proper formatting
2.1	Added text to include biopsy in assessment of TTR genetic test results. Added text to clarify that complications that will be summarized is related to transplantations. Spacing issue resolved.	Additional clarification for ease of identifying data to be analysed. Proper formatting.
5.3	Added the text “final treatment” corresponding to discontinuation of tafamidis. Added the text “Discontinuation refers to the final treatment discontinuation of tafamidis” in Figure 1. Spelling change of “analyse”	Clarification to highlight that only the last and final date of treatment discontinuation of tafamidis will be considered to identify patients in the tafamidis treated set as there could be multiple discontinuations in THAOS due to the non-interventional nature of this study. Consistency across all sections to use “analyse”.
5.4	Revised definitions of the phenotypes with consistent language used in the THAOS ad-hoc publications. Additional text added on classification of patients by liver transplant status for the	To be consistent with the new and updated definitions of phenotypes across all deliverables related to THAOS. The changes in the subgroups with liver transplant in the enrolled

PFIZER CONFIDENTIAL

	enrolled patients and the tafamidis treated patients.	set and in tafamidis treated set provides an exhaustive list of all possibilities of either having a liver transplant (prior or after) or no liver transplant.
6.1.2.2	Layout of the second paragraph changed in the form of a sentence from the previous itemized version.	To maintain consistency in formatting with sections 6.1.2.1 and 6.1.2.3.
CCI	[REDACTED]	[REDACTED]
[REDACTED]	[REDACTED]	[REDACTED]
7	Additional text and corrections on which dates and months to be used for imputing missing dates and specification of the domains for which such imputations will be applied.	To be consistent with the programming standards for imputing missing dates.
8.2	Added the text tafamidis in the last paragraph	To provide clarity that off-label usage corresponds to the study drug tafamidis.
8.2.1	Added text on discontinuation refers to both from the study drug as well as study.	To ensure completeness of summarization of discontinuation either from study drug or study.

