## 5.3 TAFAMIDIS TREATED

The tafamidis treated set will include the following:

[figure not shown]
- All available data from the enrollment date until final treatment discontinuation of tafamidis or end of follow-up in THAOS (whichever is earlier) for patients who have been enrolled in THAOS, signed the informed consent and who were on tafamidis treatment on or prior to the date of enrollment in THAOS.
- All available data from first dose of tafamidis until final treatment discontinuation of tafamidis or end of follow-up in THAOS (whichever is earlier) for patients who were not on tafamidis at the time of enrollment in THAOS but subsequently initiated treatment with tafamidis.

Note: A patient can be considered part of both the tafamidis untreated and tafamidis treated sets if the patient initiated treatment with tafamidis after beginning participation in THAOS.

The below schematic will help to better understand the patient population to be analysed:

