**Figure 1 Schematic of Patient Populations to be analysed**

**Patient population:** Tafamidis Treated (includes data in orange)  
 Tafamidis Untreated (includes data in blue; excludes data after start of Tafamidis treatment [orange] including any data after discontinuation of Tafamidis [dashed line] if patient remains in follow-up)

T is denoted as Tafamidis

Discontinuation refers to the final treatment discontinuation of tafamidis

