### **Echocardiogram**

For Echocardiogram, summary statistics for the baseline will be provided for:

- Left atrium
- Aortic root
- LV septum
- LV posterior wall

- LV diastolic diameter
- LV systolic diameter
- LV ejection
- RV free wall thickness
- Quantitative LV end systolic volumes
- Quantitative LV end diastolic volumes
- Transmitral E wave peak velocity
- E wave deceleration time
- Transmitral A wave Peak velocity
- Peak tricuspid regurgitation velocity
- Derived peak pulmonary artery systolic pressure
- Septal and Lateral Peak E, A, S
- Stroke volume
- Cardiac output

Also for the following parameters corresponding to Echocardiogram, summaries will be provided at baseline:

- Value abnormalities
- Types of value abnormalities
- Respiratory variation
- Sparkling

Echocardiogram summaries will be performed for the following sets: tafamidis untreated set with predominantly cardiac or mixed phenotype at enrollment, tafamidis treated set with predominantly cardiac or mixed phenotype at enrollment, CCI [REDACTED] and either predominantly cardiac or mixed phenotype at enrollment, tafamidis treated set for patients who switched from predominantly neurologic to mixed phenotype and tafamidis untreated set for patients who switched from predominantly neurologic to mixed phenotype.

*Note: For all the above safety events (Concomitant medications, hospitalization, AE/SAE, Deaths, Laboratory, Vitals and ECG) all events collected till last tafamidis dosing date +28 days will be summarized for the tafamidis treated set and its associated sub-sets.*

CCI [REDACTED]  
[REDACTED]  
[REDACTED]  
[REDACTED]  
[REDACTED]  
[REDACTED]

PFIZER CONFIDENTIAL

CCI [Redacted]

CCI [Redacted]

[Redacted]

[Redacted]

[Redacted]

[Redacted]

[Redacted]

[Redacted]

[Redacted]

[Redacted]

PFIZER CONFIDENTIAL

[Redacted]

CCI [Redacted]

[Redacted]

CCI [Redacted]

[Redacted]

- [Redacted]
- [Redacted]
- [Redacted]
- [Redacted]
- [Redacted]
- [Redacted]
- [Redacted]
- [Redacted]
- [Redacted]
- [Redacted]
- [Redacted]

[Redacted]

CCI [Redacted]

[Redacted]

[Redacted]

CCI [REDACTED]

[REDACTED]  
[REDACTED]  
[REDACTED]

[REDACTED]  
[REDACTED]

[REDACTED]

[REDACTED]  
[REDACTED]  
[REDACTED]

[REDACTED]

[REDACTED]  
[REDACTED]  
[REDACTED]

[REDACTED]

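### Treated-set rates per patient-year count events during tafamidis interruptions and for 28 days after the last dose, but the only person-time the SAP defines is days on drug

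*SAP*

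**What the plan says.** - **The rates.** SAP 8.2.6, Exposure, promises: "Summary of exposure-adjusted Incidence rates (per patient-year) AEs and SAE for Treatment Emergent Adverse events (All causalities) and mortality for tafamidis treated set". The Amendment 2 table gives the reason: exposure may differ between the low, high and switched dose groups.
- **The person-time.** Just before that sentence, the same subsection defines duration of exposure in years as "Sum of all non-missing days when tafamidis was taken (excluding days of other clinical trial/compassionate use participation) / 365.25". No other person-time is defined in the readable text.
- **The treated set.** SAP 5.3 includes "All available data from first dose of tafamidis until final treatment discontinuation of tafamidis", or until the end of THAOS follow-up if that is earlier. Patients already on tafamidis at enrollment start at enrollment. The note to Figure 1 adds: "Discontinuation refers to the final treatment discontinuation of tafamidis".
- **Interruptions are expected.** The Amendment 1 rationale for SAP 5.3 says "there could be multiple discontinuations in THAOS due to the non-interventional nature of this study".
- **The event window.** The note closing SAP 8.2.6, which lists AE/SAE and deaths among the items it covers, says "all events collected till last tafamidis dosing date +28 days will be summarized for the tafamidis treated set and its associated sub-sets".
- **Trial and compassionate-use periods.** These are removed from the data (SAP 2.1, Assessments) and from exposure (SAP 8.2.6), so both sides of the rate match there.
- **Survival.** SAP 6.2.1 censors treated patients at the last dose, with no 28-day extension.

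The SAP does not state the denominator of the rates in words. It does not define treatment-emergent, and it does not say whether a rate counts all events or only each patient's first.

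**The concern.** A rate per patient-year means what it says only if every counted event falls in time that is also counted. Here the event window is unbroken from enrollment or first dose to the last dose plus 28 days, while the person-time drops every day off drug. An AE during a stop that is followed by a restart enters the numerator, and so does an AE or death in the final 28 days. None of that time enters the denominator.

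These are the only exposure-adjusted safety rates in the readable SAP, and the SAP supports the final report of a study that is a commitment to the EMA. The mismatch grows with the share of time interrupted and, through the tail, with short exposure. It can therefore differ between dose groups whose unequal exposure is the stated reason for the adjustment. Other disease-modifying drugs are permitted (Protocol 9.1), so an AE in a gap spent on one of them would be counted as a tafamidis event.

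**Working it through.** The documents state no rate, event count or exposure total, so there is no figure to reproduce. The check is person-time arithmetic.

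**Inputs**
- Tail: up to 28 / 365.25 = 0.0767 year per patient (SAP 8.2.6, closing note).
- S: span in years from first dose (or enrollment) to last dose. Assumed.
- g: share of S spent off drug. Assumed.
- Time on drug: S × (1 − g).

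**Step 1: all-event rates.** With E events:
- rate as the SAP reads = E / [S(1 − g)]
- matched rate = E / (S + tail)
- overstatement = (S + tail) / [S(1 − g)] − 1

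Tail only (g = 0), every patient contributing the full 28 days:

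| Span (years) | 0.5 | 1 | 2 | 3 | 5 |
|---|---|---|---|---|---|
| Overstatement | +15.3% | +7.7% | +3.8% | +2.6% | +1.5% |

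For example, at 2 years: 2.0767 / 2 = 1.038. If half the patients contribute a tail, the figures halve.

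With interruptions:

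| Share off drug | 0% | 5% | 10% | 20% |
|---|---|---|---|---|
| No tail, any span | 0% | +5.3% | +11.1% | +25.0% |
| Full tail, 1-year span | +7.7% | +13.3% | +19.6% | +34.6% |
| Full tail, 2-year span | +3.8% | +9.3% | +15.4% | +29.8% |
| Full tail, 5-year span | +1.5% | +6.9% | +12.8% | +26.9% |

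**Step 2: illustration.** Assume 1,000 patients, a 2-year span, 10% off drug, a full tail and 0.20 events per patient-year throughout. Events = 0.20 × 1,000 × 2.0767 = 415.3. On days taken, 415.3 / 1,800 = 0.231. On matched time, 415.3 / 2,076.7 = 0.200.

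**Step 3: against a pure on-drug rate.** Keep that setting with an on-drug rate of 0.20. If the off-drug rate is 0, 0.5, 1 or 2 times the on-drug rate, the SAP figure is 0.200, 0.215, 0.231 or 0.262. If nothing happens off drug, an on-drug rate is not overstated.

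**Step 4: mortality.** A death cannot be followed by a restart. A death in a gap is therefore a death after the last dose, and it is counted only if it falls within 28 days. For deaths the unmatched events come from the tail alone, so the tail-only table is the relevant one.

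**Step 5: if the rate counts patients with a first event.** Dividing such patients by full on-drug time gives, relative to a constant true hazard λ, [1 − exp(−λ(S + tail))] / [λS(1 − g)]. With g = 10% and a full tail:

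| λ per year | Span (years) | Ratio to true hazard |
|---|---|---|
| 0.05 | 2 | 1.10 |
| 0.20 | 2 | 0.94 |
| 0.20 | 5 | 0.71 |
| 1.0 | 2 | 0.49 |

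Time after a patient's first event stays in the denominator, so for common events the bias turns downward.

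**The case against.** The strongest reply is that neither half of the mismatch is stated outright. The SAP never says that the rates divide by the exposure duration. Treatment-emergent, which qualifies the AE and SAE rates, is undefined and could be meant to confine events to on-drug time. The study is descriptive (SAP 4), no AE rates are planned for the untreated set, and survival has its own Kaplan-Meier analysis. The 28 days also agree with the minimum reporting period in Protocol 11.2.

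The denominator is indeed inferred, though strongly: the definition is the only one and it directly precedes the rates. An undefined term cannot be relied on to remove events that the closing note explicitly includes. The descriptive purpose limits the consequences, but it does not make numerator and denominator agree.

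Several stronger readings are tempting, and the documents do not support them.
- **Every treated-set rate is too high.** A group with no interruption and no post-dose follow-up has no bias, and first-event rates of common AEs can be too low.
- **The inflation is very large.** A six-month gap for every patient with 1 year on drug would give (1 + 0.5 + 0.0767) / 1 = 1.577, or +58%. Nothing in the documents suggests that every patient has such a gap.
- **Missing dosing dates shrink the denominator.** SAP 7 imputes a missing start day and other partial dates, so this is largely handled.
- **Phenotype and other subgroup rates are distorted.** SAP 8.2.6 promises these rates for the treated set, and the amendment rationale names only dose groups.
- **Long periods on a successor drug count as tafamidis time at risk.** A patient who leaves tafamidis for good adds at most 28 days. Longer gaps count only if the patient restarts.

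**Conclusion.** The point holds in a bounded form. Read as written, the SAP's event window is wider than its person-time. All-event rates are overstated against matched time wherever interruptions or a tail exist, and mortality rates through the tail.

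The tail is the only component whose length the documents give. It adds at most +7.7% at 1 year on drug, +3.8% at 2 years and +1.5% at 5 years, and less if some patients are still on drug when follow-up ends. Interruptions would be the larger driver for AEs and SAEs: about +5%, +11% and +25% at assumed off-drug shares of 5%, 10% and 20%. The true shares are unknown.

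The conclusion rests on exposure duration being the denominator and on rates that count all events. If first-event rates are meant, the direction depends on how common the event is. The sponsor already matches both sides for trial and compassionate-use periods, so this extends a principle the SAP accepts.

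**What to change.** In SAP 8.2.6:
1. Define treatment-emergent, and state whether each rate counts all events or first events. For first-event rates, use time to first event, or to the end of the window, as the denominator.
2. State the denominator and use one window for events and time. Two choices are sound: (a) first dose or enrollment to last dose plus 28 days or end of follow-up, interruptions included; or (b) on-drug days plus up to 28 days after each stop, with events in longer gaps listed separately and any other disease-modifying drug flagged. Make one primary and the other a sensitivity analysis. Both exclude trial and compassionate-use periods.
3. Keep the days-taken formula for the exposure-duration summary only.
4. Align the mortality-rate window with the death counts (last dose plus 28 days) and Kaplan-Meier censoring (last dose), and reconcile both with SAP 5.3, which ends treated-set data at final discontinuation. In choosing between (a) and (b) for deaths, note that under (a) a gap ending in a restart is time in which no counted death could occur.

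The tafamidis log of start and stop dates (SAP Table 2) already holds what is needed. The cost is SAP wording and a little programming. Under (b), some events move from the rates to a listing.

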## **9.5. Study Size**

THAOS has been open since 2007. There is no set number of patients who will be enrolled in the survey. Patients will be enrolled from different countries around the world. All patients who take part in this survey will be followed until the survey is declared complete by Pfizer (currently estimated to be the year 2023) or as long as they are able to participate, or until they withdraw consent to participate.

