8.2.5, 8.2.7	
CCI [REDACTED]
 
[REDACTED]
 
[REDACTED]
 
[REDACTED] see section 6.1.
 
Updated derivation of duration of exposure to tafamidis.
	
Descriptive nature of the study limits efficacy analysis.
 
Since a subject may participate in other clinical/compassionate trials while being enrolled in THAOS, the period of such trials needs to be excluded from the safety analysis, including exposure, hence an updated derivation for duration of exposure has been used.

CCI [REDACTED]	[REDACTED]	[REDACTED]
8.2.6	Update on survival analysis.	Moved survival analysis section to safety section in order to be consistent with section 6.2. Kaplan-Meier estimates will be provided if the number of events are at least 5.
8.2.6 (previous section 8.2.7)	Summary on dose increase/decrease/stop to be removed due to limitation in CRF.	The CRF only collects limited information for stopping tafamidis dose which cannot be attributed

		directly to whether dose was increased/decreased.
	Concomitant medications both prior to tafamidis and after tafamidis for treated patients and prior to tafamidis for untreated patients.	Added additional clarification to SAP.
	Added text to safety section: “exposure-adjusted incidence rate”. Summary of incidence rates (per patient-year) for AEs and SAE Treatment Emergent Adverse events (All causalities) and mortality for tafamidis treated set” will be provided.	Duration of exposure can be different in the low, high and switched dose groups.
	Hy’s law table to be excluded.	Hy’s law requires conditions to check whether the lab value is beyond ULN, however THAOS database does not collect records/data on the ULN values for lab parameters.
	Provide duration of exposure listing for patients who switched from 61/80 mg to 20 mg.	Sample is expected to be too small to allow for descriptive statistics. Listing will be provided.
	For all safety events (Concomitant medications, hospitalization, AE/SAE, Deaths, Laboratory, Vitals and ECG) all events collected till last tafamidis dosing date +28 days will be summarized for the tafamidis treated set and its associated sub-sets.	Added additional clarification to SAP.
CCI		

		CCI [REDACTED]
[REDACTED]	[REDACTED]	[REDACTED]
[REDACTED]	[REDACTED]	[REDACTED]
[REDACTED]	[REDACTED]	[REDACTED]

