### **4 HYPOTHESES AND DECISION RULES**

There are no hypotheses associated with this survey. All analyses will be descriptive.

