## **8 STATISTICAL METHODOLOGY AND STATISTICAL ANALYSES**

### **8.1 STATISTICAL METHODS**

The key objectives of the survey are to better understand the natural history of ATTR (hereditary and wild-type forms) and the progression of disease in this patient population. Analysis of clinical outcomes will be conducted on all enrolled patients with available data. Outcomes will be examined separately for the untreated and tafamidis treated sets, as well as for appropriate subgroups within these set. Outcomes will include results of the key clinical, functional and QoL assessments used to define progression of disease.

Data will be summarized descriptively.

Continuous variables will be summarized using descriptive statistics ie, number of non-missing values and number of missing values [ie, n (missing)], mean, median, standard deviation (SD), minimum, maximum and 10th and 90th percentile.

Qualitative variables will be summarized by frequency counts and percentages. Unless otherwise specified, the calculation of proportions will be based on non-missing values.

In case the analysis refers only to certain visits, percentages will be based on the number of patients still present in the study at that visit, unless otherwise specified. Sample size in a subgroup needs to be at least 10 in order to have sufficient data to provide descriptive statistics, listings will be provided for smaller subgroups.

Kaplan-Meier estimates (product-limit estimates) will be presented including the median time with two-sided 95% confidence intervals (CIs), if the number of events are at least 5.

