### Adverse Events & Serious Adverse Events

All adverse events will be coded according to the latest Medical Dictionary for Regulatory Activities (MedDRA) version at the time of analysis.

Adverse events (all causality and treatment-related) will be summarized by severity and starting dose using the tafamidis treated set by phenotype at enrollment and overall, CCI [REDACTED] and either predominantly cardiac or mixed phenotype at enrollment, tafamidis treated set for patients who had severe hepatic impairment at baseline, tafamidis treated set by liver transplantation status (liver transplant prior to first dose of tafamidis/liver transplant after the first dose of tafamidis/no liver transplant).

Separate summaries will be provided for all AEs, treatment related AEs, all SAEs, treatment related SAEs, AEs leading to dose reduction, AEs leading to withdrawal of tafamidis (temporarily or permanently, or delayed) and AEs leading to tafamidis dose interruptions.

Listings will be provided for adverse events corresponding to all enrolled patients and for patients with off-label usage of tafamidis. A separate listing of SAEs will also be provided for tafamidis treated set.

The following AE summary tables will be provided corresponding to some of the important potential risks using the tafamidis treated set.

- For **hepatotoxicity** using the search criteria: MedDRA SMQ (Standardized MedDRA Query) [Broad and narrow] Drug related hepatic disorders – comprehensive search. The derivations and conventions related to the search criteria will follow the programming specifications done in the Periodic Safety Update Report (PSUR) 12 for tafamidis.
- For **reproductive and developmental toxicity and lactation**:
  - MedDRA SMQ (Broad and narrow): Congenital, familial and genetic disorders; Foetal disorders; Neonatal disorders, Neonatal exposures via breast milk.
  - MedDRA Preferred terms (PTs): Exposure during pregnancy, Exposure via father, Foetal exposure during delivery, Foetal exposure during pregnancy, Foetal exposure timing unspecified, Maternal exposure before pregnancy, Maternal exposure during delivery, Maternal exposure during pregnancy, Maternal exposure timing unspecified, Drug exposure before

- pregnancy, Exposure via breastmilk, Maternal drug affecting foetus, Maternal exposure during breastfeeding
- The derivations and conventions related to the search criteria will follow the programming specifications done in the PSUR 12 for tafamidis.

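### Exposure-adjusted AE and SAE rates carry no dose split, although differing exposure by dose is why they were added, so the by-dose AE tables default to crude percentages

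*SAP*

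**What the plan says.** **The rates.** In SAP 8.2.6 (Exposure), the sentence on exposure-adjusted incidence per patient-year covers AEs and SAEs (treatment-emergent, all causalities) and ends "mortality for tafamidis treated set will be provided". It gives no breakdown by dose, phenotype or subgroup. The same subsection does state strata for duration of exposure: "by starting dose using the tafamidis treated set by phenotype at enrollment and overall", then severe hepatic impairment and liver-transplant status.

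**Why they were added.** SAP section 1, Amendment 2, gives this rationale: "Duration of exposure can be different in the low, high and switched dose groups".

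**The AE tables.** SAP 8.2.6 (Adverse Events & Serious Adverse Events) says AEs "will be summarized by severity and starting dose using the tafamidis treated set by phenotype at enrollment and overall", and adds the hepatic-impairment and transplant subgroups. It names no statistic, so the rule in SAP 8.1 applies: "Qualitative variables will be summarized by frequency counts and percentages".

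**Follow-up.** The note at the end of the Echocardiogram subsection says that, for the treated set and its subsets, "all events collected till last tafamidis dosing date +28 days will be summarized". Observation time for AEs therefore tracks time on drug.

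**The grid.** SAP 8.2.8 marks the starting-dose column for both exposure and AE/SAE, but has no row for exposure-adjusted rates.

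**The concern.** The adjustment is written for the one summary that contrasts nothing. The tables that put doses side by side do not receive it. A crude percentage counts anyone with at least one event while observed, so it rises with time on drug even when the yearly risk is the same. The 20 mg strength has been marketed much longer than 61/80 mg. In a post-authorisation safety study, readers will compare those columns. With equal true rates, 20 mg would look worse and 61/80 mg safer. Phenotype columns could inherit the effect, because the protocol ties the 2011 approval to polyneuropathy and the 2019–2020 approvals to cardiomyopathy. The problem does not depend on dose switching: it would remain if every patient stayed on the starting dose.

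**Working it through.** **No plan figure to reproduce.** There is no target size ("There is no set number of patients who will be enrolled in the survey"), and the documents give no AE rate and no mean exposure. The calculation shows what the documents' dates permit. It does not predict the result.

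**Inputs from the protocol**
- 20 mg: EU approval 16 November 2011 (7.1; strength in 7.3).
- 61/80 mg: Japan March 2019, US May 2019, EU February 2020 (7.1). Each is counted from the first of the month, which is an assumption.
- End of data collection: 16 June 2023 (section 6).

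**Longest possible commercial exposure (days / 365.25)**
- 20 mg: 4,230 / 365.25 = 11.58 years.
- 61/80 mg: Japan 1,568 / 365.25 = 4.29; US 1,507 / 365.25 = 4.13; EU 1,231 / 365.25 = 3.37 years.
- Ratio of 20 mg to 61/80 mg: 2.7, 2.8 and 3.4.

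**Crude percentage at equal true rates.** Assume a constant first-event rate λ, the same in both dose groups. Then crude percentage = 1 − exp(−λT). For example, at λ = 0.05: 1 − exp(−0.05 × 11.58) = 44.0%, and 1 − exp(−0.05 × 4.13) = 18.6%, a ratio of 2.36.

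| λ per patient-year | 20 mg | 61/80 mg (Japan / US / EU) | Ratio (Japan / US / EU) |
|---|---|---|---|
| 0.01 | 10.9% | 4.2 / 4.0 / 3.3% | 2.60 / 2.71 / 3.30 |
| 0.05 | 44.0% | 19.3 / 18.6 / 15.5% | 2.28 / 2.36 / 2.83 |
| 0.10 | 68.6% | 34.9 / 33.8 / 28.6% | 1.97 / 2.03 / 2.40 |
| 0.20 | 90.1% | 57.6 / 56.2 / 49.0% | 1.56 / 1.60 / 1.84 |
| 0.50 | 99.7% | 88.3 / 87.3 / 81.5% | 1.13 / 1.14 / 1.22 |
| 1.00 | 100.0% | 98.6 / 98.4 / 96.6% | 1.01 / 1.02 / 1.04 |

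The ratio exceeds 2 when λ is below about 0.09 (Japan), 0.11 (US) or 0.16 (EU).

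**Staggered starts.** If exposure is uniform between 0 and the maximum, crude percentage = 1 − (1 − exp(−λT)) / (λT). In the US window the ratios for the same six rates are 2.74, 2.50, 2.26, 1.91, 1.44 and 1.20. The two-fold limits move to about 0.15, 0.17 and 0.28 per patient-year.

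**Closer exposures, λ = 0.10.** Exposures of 5 and 2 years give 39.3% and 18.1% (ratio 2.17). Exposures of 3 and 2 years give 25.9% and 18.1% (ratio 1.43).

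**Rates by dose.** Expected patient-years to first event are (1 − exp(−λT)) / λ. Dividing the crude proportion by this returns λ in each group: 0.05 and 0.05, or 0.10 and 0.10, a ratio of 1.00. This follows from the constant-rate assumption. It shows that the exposure-time artefact goes, and nothing more.

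**The case against.** The strongest reply is that the sentence names a population and not a table layout. Elsewhere the SAP uses the word overall for an unsplit summary, and here it does not. The stated reason itself suggests that a dose split was intended. This stands to the extent that the defect may be an omission. A reader might infer that the sponsor decided to report pooled rates only, but the documents show just an unsplit sentence. A programmer could still follow it literally, and the grid does not correct it.

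A reader might also infer that SAEs go unadjusted, or that every subgroup column could be inflated two-fold. Neither is supported. SAEs are inside the exposure-adjusted sentence and lack only the split. The dates give a size for dose and, through the indications, a plausible one for phenotype. They give none for hepatic impairment or transplant status. Subgroups under 10 and off-label AEs are to be listed, and subgroup mortality has Kaplan-Meier estimates.

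The ceilings are not means. Entry is staggered, time for prior users starts at enrollment, and Amendment 2 cites high drop-out. That limits the size, as the working shows.

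Exposure is tabulated in the same strata, so readers can see that it differs. Mean exposure still does not give a first-event rate with the right denominator.

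The SAP also says "There are no hypotheses associated with this survey. All analyses will be descriptive", and no objective compares doses. That removes any question of a test. It does not stop side-by-side dose columns from being compared.

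Finally, dose is confounded with disease type, so rates per year would not make the columns fully comparable. This is true, and it limits interpretation without making crude percentages preferable.

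**Conclusion.** The point holds as a gap between the SAP's reason for exposure-adjusted AE and SAE rates and the strata it specifies for them. Read literally, the starting-dose and phenotype tables show only counts and percentages. The possible distortion is about two-fold or more for infrequent events, below roughly 0.1 per patient-year at full exposure. It falls to about 1.6 at 0.20 and 1.1 at 0.50 per patient-year in the US window, and nearly vanishes for a very common event or a row counting any AE. These sizes assume equal constant rates and exposure that follows the approval-date ceilings, either in full or uniformly over them. Actual exposures could make the ratio smaller. The change is a cheap improvement to the reporting, and nothing here shows that a planned result is wrong.

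**What to change.** In SAP 8.2.6 (Exposure), state that exposure-adjusted AE and SAE rates are given for the treated set overall, by starting dose and by phenotype, and for each other AE-table subgroup with at least 10 patients. Show patients with the event, patient-years and rate beside each percentage. Do the same in the hepatotoxicity, reproductive/developmental/lactation and thyroid tables. Add a matching row to the grid in 8.2.8. Add a note that the rates remove differences in exposure time but not the confounding of dose with disease type. The rationale also names a switched dose group, which has no column in tables laid out by starting dose; the SAP should say how those patients are shown.

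The cost is SAP wording and wider tables, since exposure is already to be summarised in the same strata. Rates will be unstable in small subgroups. The existing minimum of 10 patients limits that but does not remove it.
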